### *Exploratory endpoints*

- Incidence of complications such as retinopathy of prematurity, and periventricular haemorrhage
- Development at 2 years
- Bayley III score at 2 years

### 3. Research Design

It is proposed to minimise data collection requirements for this study through incorporation into routine clinical care. The data items required all form part of what would normally be recorded in a patient's case records. Hence it is proposed to obtain these from the Neonatal Network Research Database (NNRD).

The Neonatal Network Research Database (NNRD) is an electronic platform where neonatal patient data on all admissions to a National Health Service (NHS) neonatal unit in England, Scotland or Wales are recorded. Clinical data on all admissions to NHS neonatal units are entered by healthcare professionals, as part of routine clinical practice, onto electronic patient record systems at the point of care; from these data, approximately 450 data items (the Neonatal Data Set, an NHS Information Standard) are extracted quarterly to form the NNRD. Data held in the NNRD are used for audits, research, service evaluations and quality improvement projects.

A small number of additional data items not currently held in the NNRD, are required for this study. They are however all items that would normally be recorded in the patient's case notes; hence it is proposed to incorporate these into the electronic data capture system. Specific Research Ethics Approval will be sought for this study.

Multiple centres across the UK will be selected to participate. The parents of eligible babies will be approached for op-out consent for their child's data to be included in the study.

The study will continue recruiting until 1300 babies have been consented, and will remain open until 2 year follow up data has been obtained for those babies born < 30 weeks gestation. There will be no further follow up in those babies that have no data available at the 2 year follow-up.

## NNRD Fields

Surfactant can be administered prophylactically (usually within the delivery room) or as rescue (usually within the neonatal ward). If surfactant is given prophylactically, it is assumed that this is the first administration.

If administered prophylactically, it is proposed that the following data items are added under the 'NNUEpisodes-Labour & Delivery' category within the electronic record:

	Question	Answer
1	Volume of surfactant administered in millilitres (mL)	[free text box]
2	Method of surfactant administration	
 
• Endotracheal tube
 
• INSURE (endotracheal tube in place for 15 minutes or less)
 
• Thin catheter for minimally invasive/less invasive surfactant administration
 
• Other
 

3	Time of initial surfactant administration	[free text]
4	Specify any analgesics and/or sedatives used for surfactant administration (drug and dose)	[free text]

Surfactant can also be administered in a rescue setting, usually within the neonatal unit. In this setting, the frequency of administration is captured (i.e. whether this is the infant's first, second or third dose). The following fields are proposed under the 'Respiratory-Daily' category:

	Question	Answer
1	Volume of surfactant administered in first dose, millilitres (mL)	[free text box]
2	Specify the method of surfactant administration	
 
• Endotracheal tube
 
• INSURE (endotracheal tube in place for 15 minutes or less)
 
• Thin catheter for minimally invasive/less invasive surfactant administration
 
• Other
 

3	How many doses of surfactant were administered today?	[Free text box]
4	Time of initial surfactant administration	[free text]
5	Specify any analgesics and/or sedatives used for surfactant administration (drug and dose)	[free text]
6	FiO 2 at point of decision to administer surfactant	
 
• < 30 %
 
• 30- 39 %
 
• 40 - 49 %
 
• 50 - 59 %
 
• ≥ 60 %
 

### a. Comparative fields

In order to investigate whether surfactant dose affects neonatal outcomes, the following data will be obtained from the NNRDs:

	NNRD field	Purpose of using this field for this study
1	Demographics > Birth weight	Using this field alongside the volume of surfactant used, the dose of surfactant will be calculated.
2	Demographics > Sex of the baby (phenotypic)	Characterisation of cohort
3	Demographics > Gestation weeks and day	Inclusion/exclusion criteria
4	Antenatal > Were steroids given during pregnancy?	Characterisation of cohort
5	Antenatal > Number of antenatal steroid courses given	Characterisation of cohort
6	Labour & delivery > Methods of resuscitation	Characterisation of cohort
7	Labour & delivery > Drugs used during resuscitation	Characterisation of cohort
8	Labour & delivery > Was surfactant given during resuscitation?	Characterisation of cohort
9	Respiratory > Respiration: Surfactant given today	Inclusion/exclusion criteria
10	Discharge details > Discharge time and date (anonymised)	Duration of hospitalisation, age at discharge
11	Discharge details > Date of death and time - anonymised	Calculation of mortality
12	Discharge details > cause of death	Determination of outcomes
13	Discharge details > Discharge oxygen	To investigate whether the dose of surfactants can affect whether infants are discharged on oxygen.
14	Respiratory > Respiratory support device and support mode (daily)	To investigate whether using there is a correlation between surfactant dose and respiratory device
16	Discharge details > Clinical diagnoses at discharge	To correlate the dose of surfactant, and/or method of surfactant administration is related to clinical diagnoses at discharge
17	Retinopathy of prematurity > ROP stage*	To determine whether the dose of surfactant is related to the severity of retinopathy of prematurity
18	Cranial ultrasound scan > IVH**	To determine whether the dose of surfactant is related to the severity of periventricular haemorrhage

**The effect of surfactant dose on outcomes in preterm infants with RDS**

19	Medication > Drugs given on this day	To identify infants who have received surfactant during their hospitalisation period, and which surfactant To identify which infants received analgesics or sedatives on the same day as surfactant, and which babies were given postnatal steroids
20	Two year follow up > Respiratory & CVS system – On supplemental oxygen or any respiratory support?	To determine whether the dose of surfactant is related to whether the infants requires supplemental oxygen at 2 years
21	Two year follow up > Development – at 24 month corrected age***	To determine whether the dose of surfactant is related to infant development (normal or mild, moderate or severe delay).
22	Two year follow up > Bayley III cognitive, total raw score	To determine whether the dose of surfactant is related to the infant's cognitive ability

\*There are two NNRD fields for this outcome (right and left eye)

\*\*There are two NNRD fields for this outcome (right and left side)

\*\*\*There are four NNRD fields for this outcome (normal and mild, moderate or severe delay)

The full list of NNRD fields can be found in Appendix A.

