**The effect of surfactant dose on outcomes in preterm infants with RDS**

		month delay)?		QUESTION B)			12 months delay?)	
NNUAd hoc	Two Year Follow-up	Development – at 24 month corrected age. Is there severe delay (>12 month delay)?	DevelopmentSevereDelay	TPRG-SEND TWO YEAR CORRECTED AGE OUTCOME ASSESSMENT SCORE (DEVELOPMENT QUESTION C	n	0 No1 Yes9 Unknown	Specify if the child's development is correct at 24 months or if there is severe delay (>12 months delay).	Use in assessing two year health outcomes following discharge from neonatal care
NNUAd hoc	Two Year Follow-up	Bayley III – cognitive, total raw score	CognitiveeTRS	BAYLEY III COGNITIVE TOTAL SCORE	N3	0-200	Specify the total raw score as assessed using Bayley III. ( The Cognitive Scale (Cog) looks at how your child thinks, reacts, and learns about the world around him or her.( 2008, Pearson))	Use in assessing two year health outcomes following discharge from neonatal care

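### The exploratory 2-year cognitive endpoint is a Bayley III raw score, and the listed fields hold no age at assessment or age-standardised score to set it against

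*Protocol*

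**What the plan says.** The exploratory endpoints in section 2b include "Bayley III score at 2 years". The exploratory objectives relate it both to surfactant dose and to method of administration. No assessment window is given.

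Section 3a names the source field as "Bayley III cognitive, total raw score" and describes its purpose in these terms: "To determine whether the dose of surfactant is related to the infant", completed by a reference to cognitive ability. The Appendix A entry reads "Specify the total raw score as assessed using Bayley III", with allowed values 0 to 200. No scaled, composite or otherwise age-standardised Bayley score appears in either place.

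On completeness, section 3a says: "The full list of NNRD fields can be found in Appendix A".

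The neighbouring Development items are labelled "at 24 month corrected age" and are graded in months of delay. The Bayley row carries no such label.

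For the analysis, section 6 says only that the secondary and exploratory endpoints will be analysed. It gives no method for this one.

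**The concern.** A developmental raw score counts performance and makes no allowance for how old the child was when tested. A child seen a few months later is expected to score higher at the same level of ability. To read the score as cognitive ability, the analyst needs either the age at testing or a score already standardised for it.

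Neither is among the fields the protocol lists. At best, Bayley comparisons by dose or method would be less precise than they need to be. At worst, if follow-up visits tend to fall at different ages in the groups compared, part of any apparent cognitive difference would be a difference in visit timing. Without a recorded age, nobody could tell which of the two had happened.

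This goes beyond a choice of method that can wait for the analysis plan. An analysis plan works with the variables it receives, and the gap is in the protocol's specification of the data.

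**Working it through.** **Step 1: check the field lists.** The documents state no figure for this endpoint, so there is none to reproduce. The check is a row-by-row reading of the added data items in section 3, the table in section 3a, and Appendix A.

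| Needed to reference the score to age | Found? |
|---|---|
| Date of the 2-year assessment | Not listed |
| Chronological or corrected age at assessment | Not listed |
| Date of birth | Not listed |
| Age-standardised Bayley score | Not listed |
| Gestation at delivery | Listed. It gives the prematurity correction but not the age at testing |
| Any other derived age | Only from the discharge date: "Duration of hospitalisation, age at discharge" |

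The 24-month corrected age attached to the Development items is a nominal label, not a recorded age. Those items also carry their own age reference, because they are graded by months of delay. The raw score does not.

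**Step 2: loss of precision.** Let
- b = raw points gained per month of age,
- s = SD, in months, of age at testing,
- r = SD of the score among children tested at the same age.

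The documents give none of these, so all are assumptions. If age at testing is independent of ability, the total variance is r² + (b·s)², and the inflation factor is 1 + (b·s/r)².

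- b·s/r = 0.2: 1 + 0.04 = 1.04, or 4% more variance
- b·s/r = 0.4: 1 + 0.16 = 1.16, or 16% more
- b·s/r = 0.6: 1 + 0.36 = 1.36, or 36% more

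As one example, b = 1 point per month and r = 5 points give these three ratios at s = 1, 2 and 3 months.

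**Step 3: bias, if testing age differs between groups.** Let D be the difference between groups in mean age at testing, in months. The spurious difference is b·D points, or b·D/r in SD units. Take b from 0.5 to 1.5 and r from 5 to 8 (both assumed):

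- D = 0: no bias; only the loss of precision in step 2 remains
- D = 1: 0.5 to 1.5 points, or 0.5/8 = 0.06 to 1.5/5 = 0.30 SD
- D = 2: 1.0 to 3.0 points, or 1.0/8 = 0.13 to 3.0/5 = 0.60 SD

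These figures show how the effect scales. They are not estimates for this study.

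**The case against.** Three stronger readings are tempting, and the documents do not support them.

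*That age adjustment is impossible.* This takes Appendix A as truly exhaustive. The protocol calls it the full list, but the plan's own needs go beyond it. The propensity model in section 6 uses inborn status and age at first dose, yet the appendix has no inborn field and no date or time of birth. Section 3a asks for gestation in weeks and days, while the appendix lists weeks only. An assessment age could therefore reach the analyst even though it is not listed. What can be said is that it is not among the listed fields.

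*That the plan compares unadjusted raw scores between groups.* Section 6 states no model for this endpoint. Naming a source field does not fix how it will be analysed, and an analysis plan not seen here may say more.

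*That differences in testing age are being read as cognitive differences.* This needs testing age to differ by dose group or method, and nothing in the documents shows that it does. A nominal 2-year visit also limits the spread.

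It is also fair to say that the endpoint is exploratory, that the study stays open for 2-year data only on infants born before 30 weeks (section 3), and that the Development items already provide an age-referenced outcome.

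These arguments narrow the point but do not remove it. The measure the protocol names is not referenced to age, and the list it calls full supplies no means of doing so. An incomplete list is a reason to correct it, not to assume that the missing field will arrive.

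**Conclusion.** The point holds in limited form. The 2-year cognitive endpoint is specified as a raw score, and the listed fields contain neither an age at assessment nor a standardised score.

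With those fields, the certain cost is some loss of precision, unless every child is tested at the same age. Bias is conditional on testing age differing between the groups compared, and the listed data could not show whether it did. The variance increase of 4% to 36% rests wholly on the assumed ratios of 0.2 to 0.6, and the bias figures rest on the assumed slope and SD. All of them assume that raw scores rise with age over the range of visit ages.

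This is a minor improvement to an exploratory endpoint. The primary and secondary endpoints do not use the Bayley score and are unaffected. It is better settled before extraction. Section 5 provides for the original data to be destroyed after the final analysis, so an omitted age may be hard to recover. The same section excludes Trust identifiers from the study file, so site could not stand in for local visit timing.

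**What to change.** Add corrected age at the 2-year assessment to section 3a and Appendix A. An anonymised assessment date would also serve, provided corrected age can be derived from it. Supplying the age directly avoids handling further dates, although section 3a already uses anonymised discharge and death dates. Request the age-standardised cognitive score as well, if the database holds it; the documents do not say whether it does.

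State that the Bayley endpoint will be analysed on the standardised score or, failing that, on the raw score adjusted for corrected age at assessment. Summarise age at assessment by dose group and by method of administration, so that readers can see whether visit timing differed.

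The cost is one or two extra fields in the data request and one covariate in an exploratory model. If the follow-up record already holds the age or date, no new data collection is needed.

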## 4. Study Population

### a. Number of Participants

*Proposed sample size: 1300*

The study is powered based on assumed proportions requiring mechanical ventilation within 72 hours of 60% and 45% in the dosing groups 100-130 mg/kg and 170-200 mg/kg respectively. The required power is 80% with the treatment comparison being undertaken at the two-sided 5% level of significance. At the planning stage the proportions of patients falling into the two dosing groups is not known. The sample size for the propensity score matched analysis is determined by the smaller of the two dosing groups and also the ability to find a match for each infant in that group. The table below provides total sample sizes required based on the assumptions set down according to various splits for the proportions of infants in the two dosing groups. Note also that the assumption has also been made that 10% of infants will receive a dose that falls between the upper limit of the lower dose group and the lower limit of the higher dose group. We will also assume that for 25% of infants in the smaller dosing group a match cannot be found. Sample sizes for 90% power are provided for completeness.

The proposed initial sample size of 1300 covers a range of possible assumptions regarding the split across the dosing groups including 45%/45%, 40%/50% and 35%/55%. An interim evaluation of the proportions of infants who fall into the two dosing groups will be undertaken on the first 400 infants recruited into the study to provide a check of the assumed breakdown and a sample size change considered if these assumptions are not correct.

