**b. Rationale for study**

The rationale for this study is the clinical relevance of understanding whether surfactant dose affects neonatal outcomes in infants with RDS who are treated in the immediate postnatal period.

In a research environment, the dose of surfactant is rigorously controlled, usually administered at a dose of 100mg/kg or 200mg/kg. In clinical practice, clinicians more frequently follow the 'whole vial dosing' approach, where a full vial is given aiming to get as close as possible to the desired dose. Reasons for whole vial use include reduction of waste and administration of surfactant shortly after birth where an infant's weight is unknown. It is unclear whether whole vial dosing leads to under-dosing or over-dosing and whether either situation affects outcomes.

Information regarding the dose of surfactant delivered, and the method of administration, are not currently routinely recorded in the UK.

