### *ROC Analysis*

The amount of surfactant dose received (1st dose only) is potentially a key determinant of whether or not an infant requires mechanical ventilation within 4 days of birth. A ROC analysis will be undertaken to explore the ability of dose received to discriminate between those infants who do and those infants who do not require mechanical ventilation over this time period. The ROC analysis plots sensitivity against 1-specificity with points on the ROC curve (AUC) determined by varying the cut-off for dose received. Providing the AUC is greater than 0.7 an optimal cut-off for discrimination purposes will be chosen using Youden's J statistic. A one-sided p-value assessing whether the AUC is significantly greater than 0.5 will also be calculated.

The FiO2 level at the point of decision to administer surfactant is potentially a key determinant of CPAP failure resulting in the requirement for mechanical ventilation within 72 hours of birth. A ROC analysis will be undertaken to explore the ability of FiO2 level to discriminate between those infants who fail on non-invasive methods of ventilation and those infants who do not require mechanical ventilation over this time period. The ROC analysis plots sensitivity against 1-specificity with points on the ROC curve (AUC) determined by varying the cut-off for dose received. Providing the AUC is greater than 0.7 an optimal cut-off for discrimination purposes will be chosen using Youden's J statistic. A one-sided p-value assessing whether the AUC is significantly greater than 0.5 will also be calculated.

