## 7. MHRA reporting

Chiesi Limited is legally obliged to all report off-license use of any of its products to the MHRA. Any off-license use of Curosurf which is identified as part of the analysis of the raw data will be collated by the Chiesi pharmacovigilance team and reported to the MHRA. This includes the following:

- Dose of Curosurf used outside the licensed dose (100 – 200 mg/kg)
- Curosurf administered to treat RDS in a baby < 700g
- Curosurf administered prophylactically in a baby < 24 weeks or > 31 weeks gestational age

As only anonymised data will be analysed as part of this study, only aggregate data will be reported, and there will be no further follow-up to identify further information.

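### The sample-size splits leave no room for doses outside 100-200 mg/kg, and the one described full-range dose analysis is an unadjusted ROC curve

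*Protocol*

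**What the plan says.** **Sample size (Protocol, Section 4a).** The study is sized on "assumed proportions requiring mechanical ventilation within 72 hours of 60% and 45% in the dosing groups 100-130 mg/kg and 170-200 mg/kg respectively". On error rates: "The required power is 80% with the treatment comparison being undertaken at the two-sided 5% level of significance". For the middle of the range (130 to 170 mg/kg) it says: "the assumption has also been made that 10% of infants will receive a dose that falls between the upper limit of the lower dose group". The table covers splits of 45/45, 40/50 and 35/55, allows for 25% of the smaller group finding no match, and leads to a proposed initial 1300. The shares in the two groups are to be checked on the first 400 infants, and a change of sample size considered.

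**Doses outside 100-200 mg/kg.** The rationale (Section 2b) describes whole-vial dosing and says: "It is unclear whether whole vial dosing leads to under-dosing or over-dosing and whether either situation affects outcomes". Section 7 lists, among the uses to be reported to the regulator, "Dose of Curosurf used outside the licensed dose" of 100-200 mg/kg. The eligibility criteria (Section 4b) set no dose limit.

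**Analysis (Section 6).** The primary analysis compares 100-130 with 170-200 mg/kg, and its key sensitivity analysis compares the same two groups unmatched. The ROC Analysis subsection takes first dose received as the predictor of ventilation within four days and names no covariates. Its rule for a cut-off is: "Providing the AUC is greater than 0.7 an optimal cut-off for discrimination purposes will be chosen", using Youden's statistic. A one-sided test of the AUC against 0.5 is also planned, without that condition. For the secondary and exploratory objectives the protocol says only that analyses will be done.

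**The concern.** The sample-size assumptions and the reason for doing the study do not fit together. The rationale asks whether infants are under- or over-dosed and whether that matters. The planning table places every infant inside 100-200 mg/kg. Infants outside that range are eligible and count towards the 1300, but belong to neither dosing group, so each one lowers the yield of matched pairs below what the table assumes.

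The one described analysis that includes these infants is weak for the purpose in three ways.

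- **Confounding by size.** Section 3a says that dose is calculated from the recorded volume and birth weight. Birth weight is also a covariate in the propensity model. A raw-dose ROC curve therefore mixes the effect of dose with that of size.
- **One direction.** An ROC curve orders infants from low to high dose. If risk rises at both ends, the two effects pull the AUC in opposite directions and can cancel.
- **A threshold out of line with the planning rates.** The condition for choosing a cut-off asks for far more discrimination than the planned event rates imply.

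At stake are the claim that 1300 covers the 35/55 split, and whether the protocol describes an adjusted estimate of how outcome varies across the doses actually given.

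**Working it through.** **1. What the splits add up to.** 45 + 45 + 10 = 40 + 50 + 10 = 35 + 55 + 10 = 100%. The share left for doses below 100 or above 200 mg/kg is 0%.

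**2. Reproducing the table.** Inputs from Section 4a: 60% vs 45%, 80% power, two-sided 5%, 25% unmatched.

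- Per group: n = (1.960 + 0.842)² × (0.60 × 0.40 + 0.45 × 0.55) / 0.15² = 7.849 × 0.4875 / 0.0225 = 170.1, rounded up to 171.
- Total = 2n / (0.75 × share in the smaller group) = 342 / (0.75 × share). This gives 342/0.3375 = 1014, 342/0.30 = 1140 and 342/0.2625 = 1303, as stated. The same method reproduces all 12 cells.
- The 35/55 split already needs 1303, three more than 1300.
- The formula passes both groups' n (342) through the smaller group's share. Each pair supplies one infant to each group, so 171 pairs are enough.

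**3. Adding an out-of-range share.** The documents give no figure, so take a share o as an assumption and shrink every split by (1 − o). Total = 342 / (0.75 × share × (1 − o)):

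| o | 45/45 | 40/50 | 35/55 |
|---|---|---|---|
| 0% (table) | 1014 | 1140 | 1303 |
| 5% | 1067 | 1200 | 1372 |
| 10% | 1126 | 1267 | 1448 |
| 20% | 1267 | 1425 | 1629 |
| 30% | 1448 | 1629 | 1862 |

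By this method 1300 needs a smaller-group share of at least 342 / (1300 × 0.75) = 35.1%. It therefore tolerates o up to about 22% for 45/45 and 12% for 40/50, and none for 35/55.

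**4. Effect on real power.** Pairs at 1300 = 1300 × 0.75 × share × (1 − o).

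- 35/55, o = 10%: 307 pairs, power about 96%.
- 35/55, o = 30%: 238 pairs, power about 91%.
- Fewer than 171 pairs arise only if the smaller group falls below 171 / (1300 × 0.75) = 17.5% of the cohort.

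**5. AUC implied by the planning rates.**

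- Two equal groups, 60% vs 45%: sensitivity 0.60/1.05 = 0.571 and specificity 0.55/0.95 = 0.579, so AUC = (0.571 + 0.579)/2 = 0.575. Across the three splits, with or without the middle group, it is 0.571-0.575. For 60% vs 40% it is 0.595-0.600.
- Largest AUC if risk never rises with dose within 100-200 mg/kg and the band averages are as planned: 0.626, 0.632 and 0.642 for the three splits at 60/45, and 0.664, 0.668 and 0.680 at 60/40. The 35/55 case at 60/45 can be checked by hand. Give the highest-dosed quarter of the upper band (0.55 × 0.25 = 0.1375 of infants) risk 0 and all others (0.8625) risk 0.60. Non-events are 0.1375 + 0.345 = 0.4825, so AUC = 0.1375/0.4825 + 0.5 × 0.345/0.4825 = 0.642.
- With 1300 infants and AUC 0.575, the standard error is about 0.016. The 0.7 threshold is about 8 standard errors away, while 0.5 is about 4.8 away.
- Beyond 100-200 mg/kg the rates must be extrapolated, which is an assumption. Continuing the 60/45 logit slope with normally distributed dose centred on 150 gives 0.572 at SD 30 mg/kg, 0.637 at SD 60 and 0.695 at SD 100. A uniform spread over 30-400 gives 0.738. With the 60/40 slope, 0.7 is passed sooner: 0.716 at SD 80.

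**6. What the check at 400 would show.** The two bands together should hold 0.90 × 400 = 360 infants. At o = 10% they would hold 0.81 × 400 = 324. Counts of the two bands alone show that infants are missing, but not whether they lie between the bands or outside them.

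**The case against.** The strongest reply is that nothing important breaks. The protocol admits that the group shares are unknown, calls 1300 initial, and checks the shares at 400 infants with a sample-size change in reserve. Step 6 shows that the check would see a shortfall, and step 4 that the primary comparison keeps ample power even with 30% out of range. This stands. A reader might infer that the study is underpowered; the figures do not support that.

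It can also be said that the primary objective is openly a two-band comparison, that under- and over-dosing appears in the rationale and not as a listed objective, and that the secondary and exploratory objectives on dose are not limited to the two bands. Section 10 refers to a pre-agreed analysis plan, which is not at hand and may hold adjusted dose models. A reader might infer that the under-/over-dosing question goes unanswered, or that the ROC curve is the only analysis of these infants. The protocol supports only that it is the one described.

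The 0.7 condition restricts only the choice of a cut-off; the curve, the AUC and the p-value are produced regardless, and withholding a cut-off from a weak discriminator is a reasonable safeguard. Nor is the threshold strictly unreachable. The planning rates say nothing about risk outside 100-200 mg/kg, and a very wide dose spread, a steep gradient outside the range or a non-monotone pattern could exceed it.

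Finally, the documents give no frequency of out-of-range doses. Section 7 is a reporting duty and the rationale calls the matter unclear. A reader might build a scatter model around 100 and 200 mg/kg and conclude that the stated splits are unlikely; its targets, mix and spread would all come from outside the documents.

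What the reply leaves untouched is the 0% allowance, the resulting claim about 35/55, and the lack of adjustment in the described full-range analysis.

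**Conclusion.** The point holds in a limited form. The table allows 0% outside 100-200 mg/kg in a study whose own text foresees such doses. With an assumed 5-10% out of range, the table's method gives 1067-1126, 1200-1267 and 1372-1448 for the three splits, so the statement that 1300 covers 35/55 fails. It is already three short without any out-of-range share. This is a flaw in the stated assumptions; power for the primary comparison is not materially at risk.

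The described full-range analysis is a raw-dose ROC curve that is confounded with birth weight and blind to harm at both ends. On the planning rates its AUC would be about 0.57-0.60, and at most about 0.64 (60/45) or 0.68 (60/40) if risk does not rise with dose within 100-200 mg/kg. A cut-off is therefore not expected. If one did emerge, it would come from an analysis not adjusted for birth weight.

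These figures rest on the assumed range for o, on the splits shrinking in proportion, on the 25% unmatched share, and on using the 72-hour planning rates for an endpoint measured at four days.

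**What to change.** 1. **Sample-size assumptions.** State an explicit share outside 100-200 mg/kg, show the table for a range of values, and reword the claim about which splits 1300 covers.
2. **Check at 400 infants.** Tabulate all dose strata (below 100, 100-130, between the bands, 170-200, above 200 mg/kg). Run the matching without outcome data and count the pairs, which also tests the 25% unmatched assumption.
3. **Adjusted dose-response model.** Prespecify a logistic model of the primary endpoint on first dose as a restricted cubic spline, adjusted for the propensity covariates, in all infants with a recorded first dose. The NNRD Fields section lists the FiO2 item only for rescue administration, so the model needs a stated rule for infants without it.
4. **ROC curve for dose.** Keep the AUC as descriptive with a two-sided interval, and draw no cut-off from the unadjusted curve.

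The cost is one extra model, one outcome-free matching run and slightly less favourable stated sample sizes. No new data are collected. One limit remains: under whole-vial dosing, dose at a given birth weight may take few values, so overlap should be shown beside the spline and the curve read only where data support it.

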**Table: Sample Sizes under Various Assumptions**

Proportion of infants in each dosing group	45%/45%	45%/45%	40%/50%	40%/50%	35%/55%	35%/55%
Event rates	80% power	90% power	80% power	90% power	80% power	90% power
60% vs 45%	1014	1352	1140	1520	1303	1738
60% vs 40%	563	753	634	847	724	968

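### Every total in the sample-size table is about twice what its own assumptions require; the error is conservative, but the table and the basis for 1300 infants need correcting

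*Protocol*

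**What the plan says.** Protocol section 4a (Number of Participants) sets out these planning assumptions:

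- Event rates: "assumed proportions requiring mechanical ventilation within 72 hours of 60% and 45% in the dosing groups 100-130 mg/kg and 170-200 mg/kg respectively". The table adds a second scenario, 60% vs 40%.
- Required power 80%, with 90% also tabulated, and "the treatment comparison being undertaken at the two-sided 5% level of significance".
- What drives the size: "The sample size for the propensity score matched analysis is determined by the smaller of the two dosing groups", together with how many infants in that group can be matched.
- Match loss: "We will also assume that for 25% of infants in the smaller dosing group a match cannot be found".
- 10% of infants receive a dose between the two bands. The splits 45/45, 40/50 and 35/55 each sum to 90%, so this loss is already in them.

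Section 6 (Data Analysis) fixes the matching ratio at 1 to 1.

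The totals appear under "Table: Sample Sizes under Various Assumptions". From these the section concludes that "The proposed initial sample size of 1300 covers a range of possible assumptions regarding the split across the dosing groups", naming the three splits. It adds that "An interim evaluation of the proportions of infants who fall into the two dosing groups will be undertaken on the first 400 infants", with a change in sample size considered if the assumed breakdown proves wrong. No other inflation factor is given.

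**The concern.** In a 1:1 matched comparison, each matched infant in the smaller dosing group brings its own partner from the larger group. The smaller group therefore has to supply the number needed per group, not the number needed for both groups together. The printed totals look as though the two-group number was required from the smaller group alone.

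Three things are at stake. The stated basis for 1300 would be wrong. A decision on sample size after 400 infants could be taken against inflated targets. And the sponsor could not see how much further loss the study can absorb, because a two-fold margin sits unexplained inside the table.

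**Working it through.** **Step 1. Number per group.** Unpooled normal approximation: n = (z₀.₉₇₅ + z_power)² × [p₁(1−p₁) + p₂(1−p₂)] / (p₁−p₂)².

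- 60% vs 45%, 80% power: (1.960 + 0.8416)² × (0.24 + 0.2475) / 0.15² = 170.06, so 171.
- 60% vs 45%, 90% power: 227.66, so 228.
- 60% vs 40%, 80% power: 94.19, so 95.
- 60% vs 40%, 90% power: 126.09, so 127.

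**Step 2. Reproduce the printed table.** Total = 2n / 0.75 / (smaller-group share), rounded up. At 60% vs 45%, 80% power and 45/45, this is 342 / 0.75 / 0.45 = 1013.3, so 1014, as printed. The same formula gives all 12 printed cells exactly.

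**Step 3. The total that the assumptions require.** Total = n / 0.75 / (smaller-group share), rounded up. At 60% vs 45%, 80% power and 45/45, this is 171 / 0.75 / 0.45 = 506.7, so 507.

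| Rates, power | Pairs needed | Printed (45/45, 40/50, 35/55) | Required (same order) |
|---|---|---|---|
| 60 vs 45, 80% | 171 | 1014, 1140, 1303 | 507, 570, 652 |
| 60 vs 45, 90% | 228 | 1352, 1520, 1738 | 676, 760, 869 |
| 60 vs 40, 80% | 95 | 563, 634, 724 | 282, 317, 362 |
| 60 vs 40, 90% | 127 | 753, 847, 968 | 377, 424, 484 |

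**Step 4. Does another standard method explain the printed figures?** For 60% vs 45% at 80% power:

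| Method | Pairs | Totals (45/45, 40/50, 35/55) |
|---|---|---|
| Pooled variance | 173 | 513, 577, 660 |
| McNemar, independent pairs | 176 | 522, 587, 671 |
| Continuity-corrected | 186 | 552, 620, 709 |

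None comes near 1014, 1140 and 1303. At 90% power the pooled formula needs 231 pairs and gives 685, 770 and 880.

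**Step 5. What 1300 infants deliver.** Pairs = 1300 × share × 0.75, which is 438.75, 390 and 341.25, so 438, 390 and 341 whole pairs. With pooled variance, power = Φ{[0.15√n − 1.960√(2 × 0.525 × 0.475)] / √0.4875}.

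| Split | Pairs | Power, 60 vs 45 | Difference from 60% detectable with 80% power |
|---|---|---|---|
| 45/45 | 438 | 99.4% | 9.4 points |
| 40/50 | 390 | 98.8% | 10.0 points |
| 35/55 | 341 | 97.6% | 10.7 points (10.6 unpooled) |

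The printed totals of 1014, 1140 and 1303 would each yield about 342 pairs and 97.7% power.

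**Step 6. What this could mean at 400 infants.** Suppose the check showed a 30/60 split. The table's method would ask for 342 / 0.75 / 0.30 = 1520 infants, whereas the assumptions need 760. At 25/65 the figures are 1824 and 912. At those splits 1300 infants would still give 292 and 243 pairs, with about 95% and 91% power. The 80% target is met with 1300 until the smaller group falls to 171 / 0.75 / 1300 = 17.5% of infants (17.7% with 173 pairs).

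**The case against.** The strongest reply is that the error does no harm to power and that the excess may be wanted. Much of this stands.

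- A reader might infer that the protocol claims a false power for 1300, or that the study falls short of its power. The text supports neither. It says "The required power is 80"%, as a requirement, and prints no achieved power for 1300. That requirement is met at all three splits.
- A reader might infer that the 400-infant check will use the table. Section 4a gives no look-up and no decision rule, only that a change will be considered. The table is, however, the only link the protocol offers between split and total size, so the risk is a fair inference.
- Power of 98–99% should not be quoted without conditions. It assumes only the 10% and 25% losses, and the document points to others. The mITT population in section 6 needs complete data on every propensity covariate and an evaluable endpoint. Baseline FiO₂ is one of those covariates, yet the proposed prophylactic form in section 3 has no FiO₂ item. Section 7 anticipates doses outside 100–200 mg/kg, which the splits leave no room for. As an illustration with assumed rates, losing a further 20%, 40% or 50% of the 341 pairs at 35/55 leaves about 94%, 86% or 79% power. The planning rates also refer to 72 hours, while the primary endpoint is at four days.

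These losses might justify a larger study, but they do not explain the table. It is said to rest on the assumptions set down, none of which supplies a further factor, and an unstated allowance of exactly two in every cell is unlikely. That the two-group total was used for the smaller group is inferred from the exact match; the protocol does not say so.

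**Conclusion.** The point holds as an arithmetic error in the protocol. Every tabulated total is about twice what the stated assumptions need: exactly twice, before rounding up, with the unpooled formula, and 1.96 to 1.98 times with the pooled one. The error is conservative. It does not bias the comparison or leave it underpowered, and it gives no ground for saying that the protocol misreports an achieved power.

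Its consequences are a misstated basis for 1300, a hidden margin, and a possible unneeded increase after 400 infants. The power of 97.6% to 99.4% at 1300 rests on the three stated splits, a 25% match loss, no other loss, and the 60% and 45% rates applying to the four-day endpoint.

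**What to change.** - Replace the table with the required totals in step 3, or keep larger totals and name and quantify the extra allowance intended, for example for incomplete propensity covariates, non-evaluable infants or doses outside both bands.
- Restate what 1300 delivers, conditional on the split, the match rate and any further loss: about 97.6% to 99.4% power for 60% vs 45%, or 80% power for a difference of roughly 10 points from 60%, if nothing else is lost.
- Express the 400-infant check as the projected number of matched pairs, set against 171 for 80% power or 228 for 90% (173 or 231 if the pooled formula is preferred).

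The cost is a corrected table and a few sentences in section 4a. No change to enrolment is needed.
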